Study Protocol

Title: Comparison of Different Ventilator and Vaporizer Technologies to Study Economic and Environmental Implications

NCT#: 04851314

Date: 10-05-2018

[name]
Clinical Director of Neuroanesthesiology
Neuroanesthesiology Rotation Director
Clinical Competency Committee
Section Editor Engineering and Tech CSA
Associate Professor
Department of Anesthesiology
Department of Neurosurgery
Department of Neurocritical Care
UC Irvine Health

PROTOCOL NARRATIVE FOR EXPEDITED OR FULL COMMITTEE RESEARCH

University of California, Irvine Institutional Review Board

Version: April 2013

HS#: 2014-1248
For IRB Office Use Only

Lead Researcher Name: [name]

Study Title: Low-flow Anesthesia: Cost-effectiveness of the FLOW-i Anesthesia Machine, a Comparison to Established Anesthesia Delivery Unit

NON-TECHNICAL SUMMARY

Provide a non-technical summary of the proposed research project that can be understood by IRB members with varied research backgrounds, including non-scientists and community members. The summary should include a brief statement of the **purpose of the research** and **related theory/data supporting** the intent of the study as well as a brief description of the **procedure(s) involving human subjects**. ***This summary should not exceed ½ page.***

During general surgery, patients receive a series of standard medications to induce and maintain anesthesia and pain control. The anesthesia machines help deliver these inhaled anesthetics, while at the same time breathing for the patients. Most anesthesia machines have large volume breathing circuits that needlessly waste inhaled gas anesthetics. An FDA-approved FLOW-i C20 anesthesia machine uses a low volume system without large reservoirs.

The primary aim of this research is to evaluate the cost-effectiveness of the MAQUET FLOW-i C20 machine. Reducing the circuit volume can have many benefits. Most anesthesia machines require higher fresh gas flows and deliver fresh gas flow throughout the entire respiratory cycle. The Maquet machine requires significantly less fresh gas flow and only delivers fresh gas flow during inspiration. **The purpose of this study is to compare the MAQUET FLOW-i machine to high volume anesthetic machines.**

SECTION 1: PURPOSE AND BACKGROUND OF THE RESEARCH

1. Describe the **purpose of the research** project and state the overall objectives, specific aims, hypotheses (or research question) and scientific or scholarly rationale for performing the study.
2. Provide the **relevant background information** on the aims/hypotheses (or research question) to be tested and the procedures/products/techniques under investigation.
3. Include a description of the **primary outcome variable(s), secondary outcome variables, and predictors** and/or comparison groups as appropriate for the stated study objectives.
4. Include a critical evaluation of **existing knowledge**, and specifically identify the information gaps that the project intends to address.
5. Describe **previous research** with animals and/or humans that provides a basis for the proposed research. **Include references/citations**, as applicable.

This section should not exceed 4 pages.

The purpose of this study is to test whether or not the use of a low volume ventilator in an anesthesia machine reduces anesthetic costs significantly as compared to other high volume machines. The study will compare the FLOW-i anesthesia machine to a GE anesthesia machine

during routine elective general surgery in patients with ASA ratings of 1-2 under general anesthesia receiving standard care.

General anesthesia based on the administration of inhaled anesthetics is common practice. The clinical use of sevoflurane is standard of care in the operating room. There are today a variety of anesthetic devices introducing the gas in somewhat different manners. The technical solution has an impact on entire gas consumption. Techniques providing safe and effective anesthesia but with a minimum of waste is sought in order to decrease direct drug related costs.

1. **Primary study variable:** amount of gas vaporized anesthetic per minute anesthesia.
2. **Secondary study variables:**
 - a. Time to reach Aldrete > 8
 - b. Time to extubation from weaning
 - c. **Maquet firmware-based volatile anesthetic consumption data**

Sevoflurane an inhaled halogenated anesthetic has physiochemical properties promoting its use in low flow anesthesia.

Low blood gas solubility promotes in theory the use of the third generation inhaled anesthetics for use during general anesthesia with low fresh gas flow. The benefits of low blood and tissue solubility during low and minimal flow are not yet studied.

Reducing the fresh gas circuit volume has many benefits; it reduces the risk for unnecessary workplace contamination, environmental pollution and it is cost-effective. Intravenous (IV) propofol based anesthesia has become increasingly popular. The low volume inhaled anesthesia technique would assumingly also become cost-effective rivalling generic low price propofol. The simplicity to start and continuously monitor anesthetic depth which is difficult with IV anesthetics should also be recognized.

The breathing circle should attain an adequate gas mixture of inhaled; oxygen and inhaled agent as well as the absence of carbon dioxide. The anesthetic machine provides the fresh gas entering the breathing circle. The delivery of fresh gas differs between machines. The feeding of fresh gas and subsequent anesthetic vapor in to the breathing circle differs between devices. The amount of vapor introduced to the breathing circle has a major impact on the gas kinetics and subsequent need for total gas delivered.

SECTION 2: ROLES AND EXPERTISE OF THE STUDY TEAM

List all study team members below.

1. Identify each **member's position** (e.g., Associate Professor, graduate or undergraduate

student) and **department**, and describe his or her **qualifications, level of training and expertise**. Include information about relevant licenses/medical privileges, as applicable.

2. Describe each team member's **specific role and responsibility** on the study.
3. **Faculty Sponsors** - list as Co-Researchers and describe their role on the project; include oversight responsibilities for the research study.
4. Explain who will have **access to subject identifiable data**.
5. Indicate who will be **involved in recruitment, informed consent process, research procedures/interventions, and analysis of data**.

Lead Researcher:

 - a. Include an explanation of the study design (e.g., randomized placebo-controlled, cross-over, cross-sectional, longitudinal, etc.) and, if appropriate, describe stratification, randomization, and blinding scheme.
 - b. Provide precise definitions of the study endpoints and criteria for evaluation; if the primary outcomes are derived from several measurements (i.e., composite variables) or if endpoints are based on composite variables, describe precisely how the composite variables are derived.
 - c. Indicate how much **time will be required of the subjects**, per visit and in total for the study.
 - d. Indicate the **setting where each procedure will take place/be administered** (e.g. via telephone, clinic setting, classroom, via email). **Note:** *If any of the procedures will take place at off-campus locations (e.g., educational institutions, businesses, organizations, etc.) Letters of Permission are required.*
 - e. If a procedure will be completed more than once (e.g., multiple visits, pre and post survey), indicate **how many times** and the **time span** between administrations.
2. **For studies that involve routine (standard of care) medical procedures:**
Make clear whether procedures are being done for clinical reasons or for study purposes, including whether the procedures are being done more often because of the study. Use the following guidelines to determine the extent to which standard procedures and their associated risks need to be described in protocol:
 - a. If the standard procedure is not explicitly required by the study protocol, the protocol need not describe that procedure or its risks.
 - b. If the standard procedure is a main focus of the study (e.g., one or more arms of a randomized study is standard) or is explicitly required by the study protocol, the protocol must include a full description of the procedure and its risks.]
3. It is **strongly recommended** that you include a table of visits, tests and procedures. Tables are easier to understand and may help to shorten long repeated paragraphs throughout the narrative.
4. If study procedures include collecting **photographs, or audio/video recording**, specify whether any subject identifiable information will be collected and describe which identifiers will be collected, if any.
5. Describe how the **subject's privacy will be protected** during the research procedures. **Note:** *This is not the same as confidentiality (see the [Privacy and Confidentiality web page](#)).*
6. Be sure to submit **data collection instruments** for review with your e-IRB Application (e.g., measures, questionnaires, interview questions, observational tool, etc.).

The study member will screen for potential subjects using the UCIMC surgical schedule. If a subject is deemed ineligible based on the inclusion and exclusion criteria after reviewing the medical history, his/her record will be discarded. No records will be retained from ineligible subjects. After discussing with the patient's surgeon, study team member will initiate the informed consent process by approaching each eligible subject to explain the study and what it entails. The Lead Researcher will address all questions and concerns from the subject before asking the subject to sign the research consent form.

The GE anesthesia machines currently owned by the operating room will be used to serve as the comparator to the Flow-i machine. The high volume anesthesia machines do not use a low volume system. Subjects will be randomized by recruitment day. On a given recruitment day, all consented subjects will receive anesthesia from one of two groups:

- (1) MAQUET FLOW-i device
- (2) GE anesthetic device

Time points for both groups include:

T₀: Time of intubation, when volatile anesthetic are typically first delivered to the patient. We will use 15L/min fresh gas flow, while dictating tidal volumes of 6-8 mL/kg ideal body weight and a PEEP of 6 centimeters of water (cm H₂O) in accordance with current best practices.

T₁: Time of incision, which typically represents the time of reaching steady state conditions of volatile anesthetic delivery. We will reduce fresh gas flow to 2 L/min in accordance with local practice and weigh the vaporizer at this point, allowing us to measure comparative anesthetic consumption during this wash-in time period (T₀-T₁).

T₂: Time of anesthetic weaning, typically the time when preparing for patient emergence begins by discontinuing the delivery of volatile anesthetics to the patient. The vaporizer will be re-weighed at this point, allowing us to measure comparative anesthetic consumption at steady state maintenance of anesthetic depth (T₁-T₂)

Logically, we will also be able to use T₀-T₂ in order to understand total comparative anesthetic consumption.

Aside from the randomization to either Group 1 or Group 2, there will be no changes in the surgical or anesthetic procedure, including the medication or treatments given to the subjects as determined by the treating physician. All subjects will receive general anesthesia in accordance to local practice.

For this study, the vaporizer(s) will be weighed on a tared scale before research procedures commence, after induction, and when the gas is shut off during weaning of anesthesia in preparation for extubation to calculate the amount consumed during this time (grams/minute). In addition, the following variables will be recorded:

- Subject weight (kg)
- Tidal Volume (TV)
- Respiratory Rate (RR)

- Positive end-expiratory pressure (PEEP)
- Fresh Gas Flow
- Volume % gas
- End Tidal (%)
- Time of extubation
- Time when Aldrete score > 8

This is not a physician-blinded study being that the physical characteristics of the standard delivery units are distinguishable from the MAQUET FLOW-i machine.

All MAC concentrations are standard of care: After the surgical procedure, patient will be assessed for time to reach Aldrete score greater than 8, level of pain and time to extubation. Their medical records will be reviewed to determine need for times and adverse events. Patients will not be contacted for study-related follow-up after they are discharged from recovery.

No photographs or audio/video recording will be collected for this study.

Subject's Privacy:

The study team member will screen for potential subjects using the UCIMC surgical schedule. If a subject is deemed ineligible based on the inclusion and exclusion criteria after reviewing the medical history, his/her record will be discarded. No records will be retained from ineligible subjects.

Study team member will approach each eligible patient to explain the study and what it entails. The study team member will address all questions and concerns from the subjects before asking the patient to sign the research consent form.

B. Statistical Considerations

1. **Statistical Analysis Plan:** Describe the statistical method(s) for the stated specific aims and hypotheses described in Section 1. *Note: Required for scientific review.*
2. **Explain how the overall target sample size was determined** (Provide power / sample size justification for the study).

If a statistical analysis plan is not appropriate for your study design, please describe a plan for assessing your study results.

The primary purpose of this study is to evaluate the Maquet anesthesia workstation in regards to savings of volatile agent compared to conventional machines. As the Maquet workstation is more expensive than conventional machines, there must be a substantial cost-savings in terms of volatile agent to offset the additional up-front cost. The typical service life of an anesthesia workstation is around 5 years. For powering this study we decided that to be cost-effective the Maquet machines must save enough volatile agent in 1.5 years to offset the cost-difference, leaving the remaining service lifetime as profit over conventional machines.

Since volatile agent use is not recorded on a per-case basis, nor is it possible to determine from the anesthesia intra-op record, we also needed to estimate the approximate volatile use per case. Volatile use increases with length of case, fresh gas flow rate, and vaporizer percent-saturation setting. From pharmacy purchase records, we know that the average monthly Sevoflurane purchase over the past two years at UCI is $\$11,700 \pm \$6,200$. Averaged out over approximately 20 OR locations using Sevoflurane daily and about 30.5 days in a month, this gives us $\$19.2 \pm$

10.2 per OR per day cost. Finally, assuming 40 cases per day in the main OR spread over those 20 rooms gives us two cases per day on average per room, or $\$9.6 \pm 5.0$.

The cost difference in the Maquet machines is approximately \$50,000 over conventional machines, meaning the total Sevoflurane reduction must amount to \$50,000 over 1.5 years. With \$11,700 per month average over 1.5 years totaling \$210,000, a \$50,000 reduction represents about a 25% reduction in total use.

So, assuming we will have two groups (Maquet and conventional) for which we will measure Sevoflurane use during cases, the Maquet machine must use 25% less Sevoflurane to be cost-effective. With a per-case cost of $\$9.6 \pm 5.0$ for the conventional group, we must have sufficient power to differentiate whether the Maquet group has a cost of $\$7.2 \pm 5.0$ per case (assuming equal case variance for this group).

With a power of 0.8 (20% type II risk), a significance level of 0.05 (type I risk of 5%), and using a one-sided t-test to compare groups, we require two groups of 55 patients (n=110 total) in each group – Group 1: Maquet Anesthesia Machine, Group 2: GE Anesthesia Machine – to detect a 25% change in cost. An additional 11 subjects (10% attrition rate) will be included to the target sample size to account for unforeseen circumstances leading to an exclusion i.e. mechanical failure, incomplete data, different anesthetic device etc.

SECTION 4: SUBJECTS (PERSONS/CHARTS/RECORDS/SPECIMENS)

A. Number of Subjects (Charts/Records/Biospecimens)

1. Indicate the **maximum number of subjects to be recruited/consented** on this UCI protocol. This is the number of potential subjects you may need to recruit to obtain your target sample size. This number should include projected **screen failures and early withdrawals**. *Note: The IRB considers individuals who sign the consent form to be "enrolled" in the research.*
2. For **Mail/Internet surveys** include the number of people directly solicited.
3. If the study involves use of **existing charts, records, biospecimens**, specify the maximum number that will be reviewed/tested to compile the data or the sample population necessary to address the research question.

1. The maximal sample size is 128 subjects. The target sample size at UCI is 110 subjects. 55 patients for Group 1 (Maquet), 55 patients for Group 2 (GE machine)

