Coded data; code key is kept separate from data in secure location.

Data includes subject identifiable information. **Note: Encryption software is required.** (Provide rationale for maintaining subject identifiable info):

Data will be stored on secure network server.

Data will be stored on stand alone desktop computer (not connected to network/internet)

Other (specify here):

Hardcopy Data, Recordings and Biospecimens (check all that apply):

Coded data; code key is kept separate from data in secure location.

Data includes subject identifiable information (Provide rationale for maintaining subject identifiable info):

We will only maintain subject identifiable for organization purposes only. Access to this information is limited to only study team members at UCIMC and must be approved by the lead researcher. All data will be de-identified before study team conducts any statistical tests, sharing data with MAQUET for research purposes.

Data will be stored in locked file cabinet or locked room at UCI/UCIMC.

Data will be stored locked lab/refrigerator/freezer at UCI/UCIMC.

Other (specify here):

Data on Portable Devices:

4. Describe the **portable device(s) to be used** (e.g. laptop, PDA, iPod, portable hard drive including flash drives).
5. Specify whether **subject identifiable data** will be stored on the device. If so, **justify why** it is necessary to store subject identifiers on the device.

Note: Only the “minimum data necessary” should be stored on portable devices as these devices are particularly susceptible to loss or theft. If there is a necessity to use portable devices for initial collection of identifiable private information, the portable storage devices or the research files **MUST BE ENCRYPTED**, and subject identifiers transferred to a secure system as soon as possible.

Not applicable – No study data will be maintained on portable devices.

Data Access:

6. Specify who, besides the entities listed below, will have **access to subject identifiable private data and records**.
7. If there is a **code key**, specify who on the research team will hold the key, and who will have access to the key.
8. If publications and/or presentations will include **subject identifiable information**, specify where the data will be **published and/or presented** and address how the study team will obtain permission from subjects.

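### Recruitment days are randomised, but the sample size and the only named test treat the 110 patients as independent

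*Combined protocol and SAP*

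**What the plan says.** The study procedures text in Section 3 sets the allocation: "Subjects will be randomized by recruitment day. On a given recruitment day, all consented subjects will receive anesthesia from one of two groups". Every patient consented on a given day therefore receives the same machine.

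Section 3.B (Statistical Considerations) works from a per-case cost of 9.6 dollars (SD 5.0) on the conventional machine and 7.2 dollars (same SD) on the Maquet machine. With 80% power and a 5% significance level it concludes: "using a one-sided t-test to compare groups, we require two groups of 55 patients". A further 11 subjects cover exclusions such as mechanical failure, incomplete data or use of another device. Section 4.A repeats 55 per group, caps recruitment at 128, and refers back to Section 3.B for the adequacy of the sample size.

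The only figure bearing on daily numbers is the case load used for costing in Section 3.B: 40 cases a day "spread over those 20 rooms gives us two cases per day on average per room". That counts all cases, before eligibility and consent. The text gives no expected number of study patients per day, number of recruitment days, ICC, design effect or day-level analysis.

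Section 12 adds: "All data will be de-identified before study team conducts any statistical tests".

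**The concern.** When whole days are allocated, the day is the independent unit. Patients treated on the same day may share staff, room or surgical list, and so resemble one another in sevoflurane use. Section 3.B itself names vaporizer setting as a driver of use, and the study procedures leave treatment to an unblinded physician, so same-day correlation is plausible.

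A patient-level t-test ignores this. With positive correlation its standard error is too small, so a machine with no real advantage would be declared superior more often than the plan states. An analysis by day has the correct error rate but less power than the plan promises. Both matter here because the result is meant to support a purchasing argument.

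**Working it through.** **Inputs from Section 3.B.** Difference 9.6 − 7.2 = 2.4 dollars; SD 5.0; standardised difference 2.4/5.0 = 0.48; one-sided 5%; 55 per arm.

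**Assumed inputs, not in the documents.** Patients per recruitment day, *m*, taken as equal across days, and the ICC.

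**Step 1: reproduce the plan's figure.** With independent patients, the t critical value on 108 degrees of freedom is 1.659 and the noncentrality is 0.48 × √(55/2) = 2.517. Power is 80.4% at 55 per arm and 79.8% at 54. So 55 is the smallest number that reaches 80% under independence. It contains no margin for clustering.

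**Step 2: allow for clustering.**

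- Design effect: DE = 1 + (*m* − 1) × ICC.
- True size of the patient-level test: P(t on 108 df > 1.659/√DE).
- Power of a day-level test: noncentral t with 110/*m* − 2 degrees of freedom and noncentrality 0.48 × √(27.5/DE).

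Worked case, *m* = 2 and ICC 0.1: DE = 1.10. The size is P(t > 1.659/1.049 = 1.582) = 5.8%. The noncentrality is 2.400 on 53 degrees of freedom, which gives power of 76.6%.

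| *m* | ICC | DE | Size of patient-level test | Power of day-level test |
|---|---|---|---|---|
| 1 | any | 1.00 | 5.0% | 80.4% |
| 1.3 | 0.05 | 1.015 | 5.1% | 79.8% |
| 1.3 | 0.1 | 1.03 | 5.3% | 79.3% |
| 1.5 | 0.1 | 1.05 | 5.4% | 78.5% |
| 2 | 0 | 1.00 | 5.0% | 80.0% |
| 2 | 0.01 | 1.01 | 5.1% | 79.6% |
| 2 | 0.05 | 1.05 | 5.4% | 78.2% |
| 2 | 0.1 | 1.10 | 5.8% | 76.6% |
| 2 | 0.2 | 1.20 | 6.6% | 73.4% |
| 2 | 0.3 | 1.30 | 7.4% | 70.4% |
| 4 | 0 | 1.00 | 5.0% | 79% |
| 4 | 0.05 | 1.15 | 6.2% | 73.9% |
| 4 | 0.1 | 1.30 | 7.4% | 69.3% |
| 4 | 0.3 | 1.90 | 11.6% | 55.3% |

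Fractional *m* is an average, treated with the same equal-size formula.

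**Step 3: simulation check (40,000 runs per setting).** At *m* = 2, ICC 0.05, the patient-level test had size 5.4% and the day-means test had power of 77.9%. At *m* = 4, ICC 0.2, the figures were 9.7% and 61.9%. The day-means test kept its size at 4.8% to 5.1% throughout. The mean estimated difference at *m* = 4, ICC 0.3 was 0.480 for a true value of 0.48, so there was no bias.

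**Step 4: patients needed to regain 80%.** At *m* = 2: 55 × 1.05 = 57.75, so 58 per arm (ICC 0.05); 55 × 1.10 = 60.5, so 61 (ICC 0.1); 55 × 1.30 = 71.5, so 72 (ICC 0.3). The cap of 128 allows 64 per arm.

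**The case against.** The strongest reply is that the effect may be very small. Two cases per room per day is a count before the exclusions for age, BMI, ASA class, COPD and procedures under two hours, and before consent. An average of 1.2 to 1.5 study patients per day is plausible, and there the table shows shifts of a few tenths of a point in size and at most about two points in power at an ICC of 0.1. The primary variable is per minute, which largely removes case length, and fresh gas flow is set by the protocol, so two of the three drivers of use named in Section 3.B are normalised or fixed. The rows at four patients per day need more than one study room, which is not stated. All of this stands, and it limits how much weight the larger figures can bear.

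A second reply is that the t-test appears only in the sample-size sentence, so the plan never explicitly commits to it. That is fair as a reading, but it is the only test named in the section that serves as the analysis plan. Treating it as the primary test is an inference.

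A third is that the 11 extra subjects would absorb the loss. If none were lost, about 60.5 per arm would remain, enough for power up to a design effect of roughly 1.1. But they are assigned to exclusions, and extra patients do not correct the error rate of a test that uses the wrong unit.

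Finally, crossing 80% means little in itself. The plan's margin is 0.4 points, and lost degrees of freedom alone use it up at two patients per day.

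**Conclusion.** The concern holds. The mismatch between the randomised unit and the analysed unit is in the text and does not depend on any assumption. Its consequence does: it needs more than one patient on at least some days and a positive same-day correlation, and the documents quantify neither.

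In the more likely range of one to two patients per day per study room, the error rate runs from 5.0% to 7.4% and day-level power from about 80% to 70%, with the worse end reached only at an ICC of 0.3. The illustration uses the plan's SD of 5.0 dollars per case, although the primary variable is per minute; the size figures do not depend on that SD, but the power figures do. This should be fixed, but it does not invalidate the comparison.

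**What to change.** In Section 3.B:

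- Name as the primary analysis a linear mixed model with machine as fixed effect and recruitment (allocation) day as random intercept, using small-sample degrees of freedom.
- Name a t-test on day means as the alternative if the day variance cannot be estimated. Define that trigger beforehand (for example, non-convergence or an estimate of zero), because it may well occur when most days contribute one or two patients.
- Replace the single 80% by the power of 55 per arm over a declared range of patients per day and ICC.

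In Section 12, state that a non-identifying recruitment-day code stays in the de-identified analysis file. De-identification does not forbid this, but if the day is removed along with the dates, the analysis cannot be done.

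The cost is wording plus one coded variable. If the ICC is zero, the day-level test gives up about 0.5 point of power at two patients per day and 1.5 points at four. Keeping 55 per arm discloses any shortfall and does not repair it. Repair at two patients per day would take 58 or 61 per arm (ICC 0.05 or 0.1), within the cap of 128 before attrition, or 72 (ICC 0.3), above it.

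### Machines are allocated by recruitment day with no stated balancing over weekday or calendar time, so chance can leave the arms with different case mixes and cost some precision

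*Combined protocol and SAP*

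**What the plan says.** Section 3.A describes allocation in two sentences: "Subjects will be randomized by recruitment day", and "On a given recruitment day, all consented subjects will receive anesthesia from one of two groups". The form's instructions for that section ask for the stratification and randomization scheme. The response gives no blocks, strata, method of generating the sequence, concealment or planned number of recruitment days.

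Section 3.B sizes the study at 55 per group, "using a one-sided t-test to compare groups". No other analysis is named, and no adjustment for day, weekday, calendar period or type of case is mentioned. The same section acknowledges what drives the outcome: "Volatile use increases with length of case, fresh gas flow rate, and vaporizer percent-saturation setting".

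The primary variable (Section 1) is agent consumed per minute of anesthesia. Under Section 3.A, fresh gas flow is 15 L/min from intubation (T0), then 2 L/min from incision (T1) until weaning (T2). The vaporizer is weighed so that T0-T1, T1-T2 and T0-T2 can each be compared. Section 4.B excludes procedures under 2 hours and sets no upper limit.

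**The concern.** When whole days are allocated, everything that belongs to a day goes to one machine with it. Operating lists commonly recur by weekday, with the same services and surgeons; that is an assumption here, because the documents do not describe the list. If it holds, weekday determines part of the case type and length. A run of one service's days could then fall mostly to one machine, or one machine could be concentrated early in the study.

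Dividing by minutes does not remove the dependence on case length. The high-flow wash-in is a larger share of a short case than of a long one, so grams per minute over T0-T2 falls as cases lengthen. A chance difference in lists could be mistaken for a machine effect, and nothing in the stated analysis would reduce it. Analysing by day widens the interval to the right width but leaves the imbalance in place. Balancing the days reduces the imbalance itself.

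**Working it through.** **1. The plan's own figure.** Inputs from Section 3.B: means 9.6 and 7.2 dollars per case, SD 5.0 in both groups, one-sided 5% level, power 80%. The standardized difference is 2.4/5.0 = 0.48. The normal formula gives n = 2 × (1.645 + 0.842)² / 0.48² = 53.7, so 54 per group. The t-test calculation gives 54.4, so 55. The stated 55 is reproduced, with power 80.4% at 55:55 if subjects are independent.

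**2. Does case length matter per minute?** Take agent use as proportional to fresh gas flow at a fixed vaporizer setting (an assumption). For wash-in w and case length L in minutes, mean flow = [15w + 2(L − w)]/L. The wash-in time is assumed.

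| Wash-in | 2 h case | 5 h case | Difference |
|---|---|---|---|
| 10 min | 370/120 = 3.08 L/min | 730/300 = 2.43 L/min | 21% |
| 20 min | 500/120 = 4.17 L/min | 860/300 = 2.87 L/min | 31% |
| 30 min | 630/120 = 5.25 L/min | 990/300 = 3.30 L/min | 37% |

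A 2 h and a 5 h case on the same machine can therefore differ by about as much as the 25% target. This applies to T0-T2. During T1-T2 flow is 2 L/min throughout, so that comparison is less affected.

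**3. How uneven could weekdays be?** Assume each day is allocated by an independent fair coin, with days spread evenly over five weekdays.

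- Two subjects per day: 110/2 = 55 days, 11 per weekday. A split of 8:3 or worse has probability 2 × (1 + 11 + 55 + 165)/2048 = 2 × 232/2048 = 22.7% for one weekday, and 1 − (1 − 0.227)⁵ = 72% for at least one of five.
- One step further, 9:2 or worse: 2 × 67/2048 = 6.5% for one weekday and 29% for at least one of five.
- Simulated chance that at least one weekday splits 75:25 or worse: 8%, 29%, 66%, 82% and 98% at one to five subjects per day.

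**4. What does that do to the arm difference?** Let τ be the SD of the weekday means, as a share of the overall mean (assumed 10% to 20%). With D days, the SD added to the arm difference is about 2τ/√D.

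- One per day (D = 110): 0.19τ, or 1.9 to 3.8 percentage points. This is the same as randomizing individuals.
- Two per day (D = 55): 0.27τ, or 2.7 to 5.4 points.
- Three per day (D = 37): 0.33τ, or 3.3 to 6.6 points.

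For comparison, the sampling standard error from the plan's figures is 5.0 × √(2/55) = 0.953 dollars, and 0.953/9.6 = 9.9% of the mean. The SD of 5.0 is for cost per case; no per-minute SD is given.

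Part of the weekday variation is already inside that SD. The excess variance from allocating days in pairs is 4τ²/55 − 4τ²/110 = 4τ²/110, an SD of 1.9 to 3.8 points. The standard error rises from 9.9 to √(9.9² + 1.9²) = 10.1 or √(9.9² + 3.8²) = 10.6, an increase of roughly 2% to 7%.

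**5. Arm size.** At two per day, coin-flip allocation gives 66:44 or worse with probability 18%. Power from unequal size alone is 80.1% at 60:50 and 79.0% at 66:44, against 80.4% at 55:55.

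**The case against.** The strongest reply is that silence is not a design. The protocol does not say that days are allocated without restriction, and it gives neither the number of days nor the number of subjects per day. Eligibility is narrow (ASA 1-2, age 18 to 65, BMI up to 30, at least 2 hours), so about one subject per day is possible, and then little is lost. This stands. The coin flip is the working assumption behind the figures, not something the documents state. The public text also has gaps ahead of the Section 3.A response; a randomization paragraph there is unlikely but cannot be excluded.

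The 72% is also sensitive to its cut-off, since one day further gives 29%. The added noise is modest beside the sampling error. Both points stand, which is why the two probabilities and the standard error are shown together.

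A reader might infer that the comparison is biased toward one machine. The documents do not support that: days are randomized, so any imbalance is due to chance. The inferential harm comes from a subject-level t-test that ignores similarity within a day. At two per day with an assumed within-day correlation of 0.05 to 0.20, its nominal 5% error would be about 5.4% to 6.7%. Once that is corrected, what remains is precision and credibility.

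A reader might also infer that 55 per group cannot be reached. It can, by recruiting until each arm is full, although that would tend to bunch the last days on one machine. The power lost through unequal size is small in any case.

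Finally, the separate T1-T2 weighing is a partial safeguard. It does not protect T0-T2, which is the total comparison.

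**Conclusion.** The point holds as a low-cost improvement in balance and precision, not as a flaw that invalidates the comparison. Allocation is by day, no balancing over weekday or calendar time is stated, and the only named analysis adjusts for neither.

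Its size depends on two things the documents do not give: lists that recur by weekday, and about two or more subjects per day. At two per day with weekday means varying by 10% to 20%, the standard error rises by roughly 2% to 7% over individual randomization. An unlucky allocation could still move the estimate by several percentage points against a 25% target. At one per day the problem is mild. Unequal arm size is a minor matter.

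**What to change.** In Section 3.A, state that recruitment days are allocated in randomly permuted blocks of varied size within weekday (for example, in a block of four successive Mondays, two days per machine in random order), with the list concealed until the day. State the expected number of days. In Section 3.B, include weekday in the primary comparison and use an analysis that treats day as the unit of allocation.

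The cost is a different allocation list prepared before the start, and one more term in the model. No extra patients, staff or procedures are needed.

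There are two drawbacks. Late days in a block become guessable, which matters because physicians are not blinded (Section 3.A) and consent is finalised on the day of surgery (Section 5.B). Varied block sizes and concealment limit this but do not remove it. Blocking also balances days rather than subjects, so the arms should end close to 55:55 but not exactly equal.
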